“I saw a doctor at the health clinic. He told me I had a common illness called depression and that treatment could help. So I started to see someone at the clinic each week for “talk” therapy. This treatment helps me learn to control depression in my everyday life. It has taken some time, but I'm finally feeling like myself again.”

Many people who have depression know something is wrong but don't know what to do about it. This booklet can help. It tells you about four steps you can take to understand and get help for depression.

Four steps to understand and get help for depression:

- 1 Look for signs of depression.
- 2 Understand that depression is a real illness.
- 3 See your doctor. Get a checkup and talk about how you are feeling.
- 4 Get treatment for your depression. You can feel better.

Step 1

Look for signs of depression.

Read the following list.

Put a check mark by each sign that sounds like you:

- I am really sad most of the time.
- I don't enjoy doing the things I've always enjoyed doing.
- I don't sleep well at night and am very restless.
- I am always tired. I find it hard to get out of bed.
- I don't feel like eating much.

- I feel like eating all the time.
- I have lots of aches and pains that don't go away.
- I have little to no sexual energy.
- I find it hard to focus and am very forgetful.
- I am mad at everybody and everything.
- I feel upset and fearful, but can't figure out why.
- I don't feel like talking to people.
- I feel like there isn't much point to living, nothing good is going to happen to me.
- I don't like myself very much. I feel bad most of the time.
- I think about death a lot. I even think about how I might kill myself.

If you checked several boxes, call your doctor. Take the list to show the doctor. You may need to get a checkup and find out if you have depression.

Suicide

Sometimes depression can cause people to feel like killing themselves. **If you are thinking about killing yourself or know someone who is talking about it, get help:**

- Call 911.
- Go to the emergency room of the nearest hospital.
- Call and talk to your doctor now.
- Ask a friend or family member to take you to the hospital or call your doctor.

Step 2

Understand that depression is a real illness.

Depression is a serious medical illness that involves the brain. Depression is not something that you have “made up in your head.” It’s more than just feeling “down in the dumps” or “blue” for a few days. It’s feeling “down” and “low” and “hopeless” for weeks at a time.

About 19 million Americans have depression. It can happen to anyone, no matter what age you are or where you come from.

Depression can make it very hard for you to care for yourself, your family, or even hold down a job. **But, there is hope.** Depression can be treated and you can feel better.

What causes depression?

You may want to know why you feel “depressed.” There may be several causes.

- Depression may happen because of changes in your brain.
- Depression runs in some families. This means that someone in your family such as a grandparent, parent, aunt, uncle, cousin, sister or brother may have depression.
- Sometimes painful events or losses such as deaths can lead to depression.
- Sometimes the cause of depression is not clear.

Step 3

See your doctor.

Don't wait. Talk to your doctor about how you are feeling. Get a medical checkup to rule out any other illnesses that might be causing signs of depression. Ask if you need to see someone who can evaluate and treat depression.

If you don't have a doctor, check your local phone book. Go to the government services pages (they may be blue in color) and look for "health clinics" or "community health centers." Call one near you and ask for help.

Step 4

Get treatment for your depression. You can feel better.

There are two common types of treatment for depression: (1) medicine and (2) “talk” therapy. Ask your doctor which type is best for you. Some people need both treatments to feel better.

Medicine

- Medicines for depression are called “antidepressants.” Your regular doctor or a **psychiatrist** (a medical doctor trained in helping people with depression) can prescribe them for you.
- Antidepressants may take a few weeks to work. Be sure to tell the doctor how you are feeling. If you are not feeling better, you may need to try different medicines to find out what works best for you.

- Medicines sometimes cause unwanted “side effects.” You may feel tired, have blurred vision, or feel sick to your stomach. Tell the doctor if you have these or any other side effects.

“Talk” therapy

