 - You may find that answering questions about parenting your baby is helpful and interesting.
 - You will have the iPhone with free data, texting, and calls to use during the study.
 - You will be able to keep the iPhone upon completion of the study. Although we will not continue to pay for phone service, you can use the phone through wireless Internet if you have access to it.
 - You will have the videos on the iPhone that you created during on the program.
 - You will be helping researchers to learn whether the program you receive is helpful for mothers of infants.
- There are few risks to being in the program.
 - You may feel uncomfortable answering some of the questions asked today or during the project. You can stop this call at any time and skip any questions during the project that you do not want to answer.
 - All information we collect is stored in a secure, locked office or database that is only accessible by approved research staff. We will use a study number rather than your name on all study records. There is only one code sheet use to identify research participants and it is stored securely in a password-protected file on a locked computer in a locked office.
- If you have any concerns or complaints, you can find IRB contact information at gsu.edu/irb

Does this sound like something you might be interested in hearing more about?

- If no: select DECLINE for final status and Eligibility Status; in the reason box next to Eligibility Status, select TOO BUSY/TIME or NOT INTERESTED
 - Do you have any other questions I could answer for you?
 - Thank you for your time. If you change your mind, feel free to contact me in the future to see if we are still recruiting.
- If yes, continue

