- c. *We will begin the questionnaire going through questions together.* Start the questions together. Read each question for mom and allow her to choose an answer. Pay attention to how mom is doing comprehending questions and answers.
 - i. If she seems to be comprehending well, find a good point to ask if she would like to continue on her own or continue going through together. If she wants to continue on her own, remind her to stop at the pictures so you can review instructions.
 - ii. If she seems to be comfortable going through questions together, continue that way.
6. When mom reaches STOP sign she will hand iPad back to assessor. Click submit to check for safety concerns and skipped questions.

CHECK QUALTRICS FOR POTENTIAL SAFETY CONCERNS & SKIPPED QUESTIONS

1. When mom hands back the iPad, click 'Next' to see flagged questions related to self-harm.
 - a. If self-harm question(s) are endorsed, use Decision Tree to follow up.
 - i. ATQ #6 – I don't think I can go on
 - responses of moderately often, often, or all the time
 - ii. PHQ9 #9 – Thoughts that you would be better off dead, or of hurting yourself
 - responses of several days, more than half of the days, or nearly every day
 - b. NOTE: If someone is in immediate crisis, call your supervisor. Do not leave the home.
2. Check Qualtrics report for missing or skipped items. Tell mom you want to double check any missing responses and make sure nothing was skipped by mistake.
 - a. If questions were skipped on purpose, leave blank.
 - b. If questions were skipped my mistake, add the mom's new responses (edit survey option).

PREPARE FOR VIDEO RECORDING

1. *Now we are going to make a video of you and your baby as you interact together. There will be two parts to the video. We'll start with whatever you and your baby want to do together, then I'll share some books that you and your baby can look at together.*
2. Setting up for the interactions:
 - o **Setting the Stage:**
 - i. **Let mom know that we need a relatively quiet place with plenty of light.**
 - o The space should be **away from others** so that the interactions will not be interrupted by other people in the home
 - o If possible, pick a room **away from sources of noises** that could be picked up on the camera's microphone (**like a noisy kitchen, television, or street**)

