 - c. 2 video recordings
 - d. Confirm Family information and alternative contacts
3. Share materials with mom if necessary per safety decision tree
 - a. Referral to talk with doctor and/or home visitor (if PHQ9 score is 10+)
 - b. Postpartum Depression Facts
 - c. Crisis Help Card (if flagged item(s) on questionnaire were endorsed)
4. Schedule training visit to bring her iPhone to get her started in the program. NOTE: allow more time if she is in crisis or other anomalies arise that may require more time to sort out. She should plan for 1.5 hour for training – preferably when baby is asleep or another adult is at home to help with other children.
 - a. Open Google Calendar on iPad
 - b. Ask mom for best times for future calls or visits. Schedule day and time if possible and add to Google calendar using ID number ('Training Visit ID ####')

c. Confirm with mom the best numbers to call with a visit reminder or to schedule training visit (if unable to schedule now)

AFTER HOME VISIT

1. Update Access Database:

a. If applicable, update “Best times to call” under Notes in the “Tracking Information Form”

If this is a new Mom, you can click in the Date Received box and start entering data.
If this is an existing Mom, use the drop down box to the right to look up Mom's

Mom ID	(New)	Date Received	Referral Source
Study Status		Attrition Reason	Please specify other:
Mom First Name		Mom Last Name	Marital Status
Street Address		Other Address	Cell Phone
City		State	Home Phone
Mom Birthdate		Postal Code	Primary Language
Baby's Name		Baby's Birthdate	Work Phone
Email			
Notes			
Mom Baby Net App Tracking Information			
UserName:  Password: 			

b. Update Scheduled Appointments: Change “Status” from “SCHEDULED” to “COMPLETE.” Check the boxes “Q1” and “Interactions” accordingly.

Scheduled Appointments

Mom ID	Type	Date	Appointment Details	Assessor	Status	Check the Completed Assessments	Notes
101	Pre	4/8/2015	9:00 AM	[name]	Scheduled	   	
*					Completed	   	
*					Cancelled	   	
*					Rescheduled	   	

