i. Use “Notes” for things like missing data, etc., NOT safety concerns.

Initial Visit

Mom ID	Initial Visit Date	Assessor	Eligibility Status	Reason	Notes
101					

Scheduled Appointments

Mom ID	Type	Date	Appointment Details	Assessor	Status	Check the Completed Assessments	Notes
101					Scheduled	   	

ii. Complete a new line for the training visit (if scheduled).

3. Update Matriculation Table (on Google docs)

4. Complete Assessment Summary & Risk Identification (ASRI)

a. If any concern may qualify as an Adverse Event (AE) or a Serious Adverse Event (SAE): **contact [name] immediately.** The PI needs to be notified immediately. In the event of an SAE, a

letter needs to be sent out within 24 hours of the reported situation. If [name] is not in the office, send her a text to [contact].

- i. You will need to provide the supervisor with a copy of all related Safety forms
- ii. **If any safety concerns are noted, you will need the supervisor's signature on the ASRI and any and all safety forms prior to scanning**
 1. If the supervisor is not in the office you will need to obtain an electronic signature by emailing the needed documents to the supervisor in Word format.
 - iii. Add the possible AE/SAE to AE SAE Log (on Google docs)
- b. Scan the ASRI in **one PDF file** after needed signatures are obtained.
 - i. ASRIs without potential safety concerns can be scanned without supervisor signature.
 - ii. The scan, with no identifying information, should be emailed to yourself.
 - iii. Save scanned ASRI and all other documentation in the participant's ID folder in this location:
S:\ECSEHP\Projects\Baby-Net Depression NIH R01 2016-2021\Participant Data

Use this naming convention: [ID] PRE/POST [document] mm-dd-yy
Example: 101 PRE ASRI 10-22-17
 - iv. Email scanned ASRI to project coordinator

*** NOTE: If the assessment visit is completed in two visits, one final ASRI will be scanned and saved after the second visit. Be sure to enter both dates of the visits on the ASRI and what was completed by the mom and anything and everything that you responded to at each time point. If there is any concern involving potential harm- self-harm, child maltreatment or other harm, follow the protocol and send an ASRI for each visit.*

5. Project coordinator will export the PDF of mom's questionnaire responses.

- a. Save in the participant's ID folder in this location:

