Assessment Notes/Important Information about the family:

Elevated PHQ9 score? Yes No PHQ9 Total Score: _____

Depression resources provided Crisis Help Card provided

Referral to doctor or home visitor

Assessor/Coach Initials: _____

Risk Identification:

ATQ question #6 endorsed I don't think I can go on

PHQ9 question #9 endorsed Thoughts that I would be better off dead, or of hurting myself

Self-Harm

No plan, no intent to harm self, identifies reasons to not harm self

Lacks clear plan, states would not carry it out, identifies reasons to not harm self*

Has clear plan, means to harm self, cannot identify reasons to stop from harming self*

EMS Called* Participant called GA Crisis Line*

Contacted PI*

Child Abuse/Neglect

RPNI Completed* Safety information provided

Mandated Report Made*

Intimate Partner Violence

EMS called* Safety information provided

Referral to doctor or home visitor

Other Harm _____

Other: _____ **None**

**Must record in AE/SAE Log (on Google docs)*

Consult Needed: Yes No Date/time supervisor was consulted: _____
if you identified any risk above, a consult is needed

Is this a possible AE or SAE? Yes No AE/SAE #: _____

Report of clinical issue being addressed (List each issue one at a time and how it was addressed):

Report of consultation (what information was given to supervisor, what action needs to be taken, how did participant respond, what intervention was implemented, etc.):

Supervisor Comments (follow up steps needed, additional information, etc.):

Assessor/Coach Signature

Date

Supervisor Signature

Date

When complete, scan and email to [name] for filing and circulation to project team

Assessment Data Checklist

ID#: _____

PRE

POST

Date: _____

Before you leave the home:

Sprint signal: Successful Unsuccessful/Ineligible N/A

Questionnaire: Part 1 Part 2 Checked for missing data

Observation data

ASRI: Followed up for any endorsed safety questions

Safety Monitoring Forms (only used for participants with potential safety concerns)

iPhone Customization Questionnaire

Changes in Contact Information _____

Best times for calling to schedule/confirm training visit _____

Initial and date when items are complete: Initials: _____ Date: _____

At the office:

Enter Assessment Information into Access Database (S: drive)

Update Matriculation Table (Google docs)

Assessment Summary & Risk Identification completed and signed

- Email to supervisor if there is a safety concern

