- Ask mom about any new behaviors that she has seen in her behavior this week
- What is she celebrating - what milestones has she been watching for?

4. Create plan for next session

- Review mom's concise plan for the completing next session
- Review the time for your next call

5. Conclude Session with Reminder

- Help mom add the appointments to her calendar and set reminder for completing next session and having next call
- Set reminder in your calendar to send mom encouraging text the day before to complete next session & remind about next call

[date]

Dear [participant name],

I missed you at the time of our last scheduled appointment on [date]. I sent you coach notes on [dates] and have reached out to you on your project phone number as well as your preferred other contact numbers, but have not been able to reach you [as it seems that (if applicable, specify the issue- disconnected phone, full VM, etc)]. I hope that you receive this note with a reminder of my contact numbers and that all is well. I want you to know that I am here to support you however you would like to proceed, either in continuing in the intervention or discontinuing. Either way, please contact me (see contact information below) to let me know your preference for continuing in the intervention or whether you are ready to stop intervention and complete the post-assessment. If I don't hear back from you by [date], I will understand that you may not be interested in continuing the intervention at this time. I look forward to hearing from you.

[coach's name]

Mom & Baby Net Project
Georgia State University
Mark Chaffin Center for Healthy Development

(office) [coach's office number]

(cell) [coach's cell number]

(email) [coach's email address]

IV. Safety Monitoring Documents

Risk of Self Harm – Decision Tree

RESPONDING TO DEPRESSION AND POSSIBLE SUICIDE RISK

If person reports thoughts of death/suicide (ATQ #6 or PHQ9 #9 or spontaneously)

Check for a plan and protective factors:

"I noticed that you agreed with the statement..." "I'd like to talk with you a little more about that. Have you actually had any thoughts of harming yourself?"

If "Yes" ask:

- What kinds of thoughts have you been having?
- Have you thought about how you might do that? How?
- Do you have access to that (method mentioned -e.g., gun, pills, etc.)
- Have you thought about where you might do that/Where?
- Any things keeping you from carrying out plan? What? Anything Else?

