If there is a **clear plan and no protections** (E above), proceed to **Box #1**.

If there is a **plan but person identifies protections from acting** (E above), proceed to **Box #2**.

If the person **has no plan, says they would not act** on the plan, and can **tell you why** they wouldn't act on the plan (e.g., I would never do that to my baby. I couldn't stand the thought of her not having a mom), let mom know "**I am glad to hear that!**" then proceed to **Box #3**.

1. Highest Risk:

Person states that:

- They are thinking about suicide
- They have a clear plan (how, when, where)
- Means are available (guns, pills, nobody home, etc.)
- They cannot identify things stopping them from carrying out their plan

2. Medium Risk:

Person acknowledges thoughts about suicide but

- Lacks a CLEAR plan
- States that they would not carry it out and identifies reasons why they wouldn't

3. Lowest Risk:

Person is showing signs of depression but denies any thoughts about self-harm/suicide OR

- Has had thoughts but **NO plan** and says they would **not do it** and identifies reasons why they wouldn't

- Do Not leave person alone unless your safety is threatened
--Text and Call your supervisor until you make contact (wait at least 30 minutes before intervening)

- If your safety is threatened, go to nearest safe place, call 911 & state exact concern
--Text and Call your supervisor for immediate support
--Do not leave until told by EMS that they do not need to speak to you at the scene.

3. If you cannot reach a supervisor and must intervene, do the following:

- Stay calm, be empathetic, and state your concern ("I'm concerned about your safety")
- State that the person needs to "see a doctor right away" /can share "Postpartum Depression Facts & Stories" and "Crisis Help Card"
- Give 3 choices and follow through
 - They can call 911 and ask for a ride to nearest hospital for emergency behavioral health services to find a way to feel better/not hurt self
 - You can place the call to 911
 - They can have another adult join the 2 of you and the other party can sign notification form to get help.
 - They can call the Georgia Crisis & Access Line [name]

- Use gentle, reflective & empathetic statements. Be clear that you are "not a therapist, but there are people out there who can help." Share "Postpartum Depression Facts & Stories" and encourage the person to share booklet with and talk to doctor.

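### A deliberately declined self-harm item (PHQ9 #9 or ATQ #6) is left blank like any other, and the blank itself triggers no self-harm inquiry and no required supervisor review

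*Protocol*

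**What the plan says.** The in-home procedure (Protocol, Part II, the step on checking Qualtrics for safety concerns and skipped questions) has two parts. The first is the safety check: "If self-harm question(s) are endorsed, use Decision Tree to follow up". It names three qualifying response categories for each of ATQ #6 and PHQ9 #9. The second is a completeness check on all items. The assessor raises missing answers with the mother and fills in those missed by accident. For the rest the rule is "If questions were skipped on purpose, leave blank". Neither part singles out the two self-harm items.

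The recruitment scripts (Part I, and the remote counterpart in Part VI) tell mothers that they may "skip any questions during the project that you do not want to answer".

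The Decision Tree (Part IV) has the entry line "If person reports thoughts of death/suicide (ATQ #6 or PHQ9 #9 or spontaneously". Its lowest-risk box begins "Person is showing signs of depression but denies any thoughts about self-harm/suicide", with thoughts but no plan as the alternative.

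On the Assessment Summary & Risk Identification form (ASRI), the item boxes record endorsement, as in "PHQ9 question #9 endorsed", and a consult is needed when a risk has been identified. After Home Visit, item 4, adds: "ASRIs without potential safety concerns can be scanned without supervisor signature".

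The remote checks (Part VI, Pre-Assessment Call 6a xii and 6b xi; Post Assessment Call 5a xii and 5b xii) act on PHQ9 #9 codes 1 to 3 and ATQ #6 codes 3 to 5.

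**The concern.** Every mother enters on a positive depression screen, and these two items are the scheduled self-harm questions at each assessment. Because mothers are told that they may skip anything, a declined item is foreseeable. A refusal to answer a question about suicide is not the same information as a negative answer, yet the written steps let it pass with the same consequence. If the mother volunteers nothing, staff can follow the manual exactly and the supervisor need never learn that the question went unanswered.

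The main stake is safety. There is also a reporting stake: the Adverse Event Guidelines count onset or worsening of suicidal ideation as an adverse event, so an inquiry that is never made could leave such an event unrecorded.

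**Working it through.** There is no plan figure to reproduce and no rate to compute. The check is a trace: take a mother who deliberately declines PHQ9 #9 or ATQ #6 and volunteers nothing, and ask of each written step whether the blank starts it.

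| Step | Where | What starts it | Does the blank start it? |
|---|---|---|---|
| Query about missing answers | Part II, Qualtrics check, step 2 | Any missing answer | Yes, but it asks only whether the skip was a mistake |
| Decision Tree after home survey | Part II, Qualtrics check, step 1 | Named responses on either item | No |
| Four remote survey checks | Part VI, steps listed above | PHQ9 #9 codes 1–3; ATQ #6 codes 3–5 | No; blanks are not mentioned |
| Decision Tree entry | Part IV | Thoughts reported, by item or spontaneously | No |
| The tree's three risk boxes | Part IV | Thoughts with a clear plan; thoughts without one; denial, or thoughts with no plan | No; silence is none of these |
| Crisis Help Card | Part II, Before Leaving the Home, 3c | Endorsed item | No |
| ASRI consult line | ASRI form | Identified risk | No |
| Supervisor signature | Part II, After Home Visit, 4 | Safety concern noted | Only if staff choose to note one |
| Remote consultation e-mail | Part VI, after-call steps 2a ii (pre) and 7a ii (post) | Self-harm endorsed | No |
| Data Checklist, safety line | Assessment Data Checklist | Endorsed safety question | No |

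Counts from the text:

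- Survey checks: 1 (home) + 2 (remote pre) + 2 (remote post) = 5. With the Data Checklist, 6.
- Checks that mention skipped or missing answers: the home check and the Data Checklist's general missing-data tick = 2 of 6.
- Checks that give a declined PHQ9 #9 or ATQ #6 its own handling: 0 of 6.
- Decision Tree boxes that fit a non-answer: 0 of 3.
- ASRI: 2 endorsed boxes, 3 self-harm level boxes, 0 declined boxes, and an open line for other matters.

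The 0 of 6 shows where one omission recurs. It is not six separate failures, and it does not measure frequency.

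Whether an elevated total would catch the same mother depends on her score. The Recruitment Form admits on PHQ9 of at least 10, PHQ2 of at least 3, or Edinburgh of at least 11, so a PHQ9 total of 10 is not an entry condition. By the post assessment a mother's total may also have fallen.

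**The case against.** The strongest reply is that the manual has other routes to the supervisor, and that one of them needs no endorsed item. The action text printed after the Decision Tree boxes includes a script for a mother whose results suggest depression. It requires an ASRI entry and an e-mail to the supervisor, chased by text and phone if no signature comes within 24 hours. The tree's title covers depression as well as suicide risk, and Before Leaving the Home, item 3, places the PHQ9 10+ referral under the tree. On that reading, a mother with an elevated score who declines the item would still be brought to the supervisor.

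This stands in part. The script apparently belongs to the lowest-risk box, but the layout is flattened in the text, so the link is an inference. That box requires a denial, or thoughts without a plan. The trigger is signs of depression, and nothing in the script asks staff to report the blank.

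Other mitigations are also real but partial:

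- In the remote flow an elevated PHQ score obliges the coach to ask about discussions of mood with a doctor (Pre-Assessment Call 6a xii; Post Assessment Call 5a xii).
- The other self-harm item may be answered. Remotely it sits in the other survey, scheduled for another day, although a focused mother may continue on the same call.
- Staff may use the ASRI's open line or notes, and a noted concern needs a signature.
- Weekly coach calls continue, but neither call guide contains a self-harm question.

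A reader might infer that a blank prompts nothing at all. The documents do not support that: at home visits the blank itself prompts a conversation, though one limited to whether the skip was accidental. Nor do they support the inference that supervisor review is ruled out. It is not required because of the blank, but it can follow from an elevated score or from staff judgement.

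**Conclusion.** The point holds in this form: the blank itself leads to no self-harm inquiry and no required supervisor review, and the remaining safeguards turn on depression signs, an elevated total or discretion. The exposed case is a mother whose total is not elevated, who declines the item and who volunteers nothing. She may reach none of them.

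This is more than absent detail, because a stated rule directs staff to leave the blank as it is. It should be corrected, but it is a partly mitigated gap rather than a failure of the whole safety system. Its size in mothers is unknown, since the documents give no rate of declined items. The conclusion assumes only that staff do what is written and no more.

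A reader might also infer that an incomplete PHQ9 would be misread as not elevated. That depends on how the total is scored when an item is missing, which the documents do not state, so it forms no part of this point. The right to skip questions is not at fault and should stay.

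**What to change.** Add one line to each of the five survey-check steps (the Part II Qualtrics check, and the two pre and two post checks in Part VI):

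> *A blank on PHQ9 #9 or ATQ #6 is not a negative answer. The mother may decline. Mark it on the ASRI and tell the supervisor at the same contact.*

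Add a box for not answered or declined beside each of the two items on the ASRI. Make either box require supervisor review by matching edits to the ASRI consult line, the signature rule in After Home Visit, and the two remote consultation e-mail rules. The supervisor then decides what follows.

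The drafting cost is five lines, two tick boxes and those edits. Remote coaches already open the relevant Qualtrics columns, so they need no new look-up. The running cost is some additional supervisor reviews, in a number that cannot be stated without a rate of declined items.
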